#### **8.4.2 Clinical Laboratory and Vital Signs**

Clinical laboratory data (hematology, blood chemistry, and urinalysis) and vital signs will be summarized using descriptive statistics at baseline and each timepoint. Listings will display laboratory data at each period/timepoint collected by subject.

### **8.5 Pharmacokinetics**

Blood samples will be obtained for pharmacokinetics of EBP-994 at Study Visit 1 (Day 1) and Study Visit 6 (Day 28).

The following pharmacokinetic parameters will be calculated for EBP-994 on Day 1 using non-compartmental analysis, when applicable.

$AUC_{0-t}$ :	The area under the plasma concentration versus time curve, from time 0 to the last measurable concentration, as calculated by the linear trapezoidal method.
$AUC_{\text{inf}}$ :	The area under the plasma concentration versus time curve from time 0 to infinity. $AUC_{\text{inf}}$ is calculated as the sum of $AUC_{0-t}$ plus the ratio of the last measurable plasma concentration to the elimination rate constant.
$AUC/AUC_{\text{inf}}$ :	The ratio of $AUC_{0-t}$ to $AUC_{\text{inf}}$ .
$C_{\text{max}}$ :	Maximum measured plasma concentration over the time span specified.

---

$t_{max}$	Time of the maximum measured plasma concentration. If the maximum value occurs at more than one time point, $t_{max}$ is defined as the first time point with this value.
kel:	Apparent first-order terminal elimination rate constant calculated from a semi-log plot of the plasma concentration versus time curve. The parameter will be calculated by linear least-squares regression analysis using the maximum number of points in the terminal log-linear phase (e.g. three or more non-zero plasma concentrations).
$t_{1/2}$ :	Apparent first-order elimination half-life will be calculated as $0.693/kel$ .
CL/F:	The apparent total body clearance after extravascular administration, calculated as Dose/AUC inf
$V_{area/F}$ :	The apparent total volume of distribution after extravascular administration, calculated as Dose/(AUC inf x kel)

No value for kel, AUCinf or  $t_{1/2}$  will be reported for cases that do not exhibit a terminal log-linear phase in the concentration versus time profile.

Other PK parameters may be calculated if deemed appropriate.

The following pharmacokinetic parameters will be calculated for EBP-994 on Day 28 using non-compartmental analysis, when applicable.

$AUC_{0-t}$	The area under the plasma concentration versus time curve over the dosing interval at steady-state, as calculated by the linear trapezoidal method.
$C_{max,ss}$	Maximum measure plasma concentration over the time span specified.
$C_{min,ss}$	Measured plasma concentration at the end of the dosing interval.
$t_{max,ss}$	Time of the maximum measured plasma concentration. If the maximum value occurs at more than one time point, $t_{max}$ is defined as the first time point with this value
Flux	Percent fluctuation will be calculated as follows: $\frac{(C_{max} - C_{min})}{C_{ssav}} \times 100$ where $C_{ssav}$ is calculated as the ratio of $AUC_{0-t}$ to the dosing interval, $t$ .
Swing	Percent fluctuation will be calculated as follows: $\frac{(C_{max} - C_{min})}{C_{min}} \times 100$

where  $C_{ssav}$  is calculated as the ratio of  $AUC_{0-t}$  to the dosing interval,  $t$ .

Other PK parameters may be calculated if deemed appropriate.

Compartmental analysis may be performed, if deemed necessary.

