## 1.2 *Anticipated Risks To Subjects*

### Preclinical Safety Summary

Toxicokinetic data to support the toxicology program for the development of EBP-994 were obtained from three- and six-month toxicity studies in rats (19, 20), three-month and 12-month toxicity studies in cynomolgus monkeys (21, 22), and an embryo-fetal developmental toxicity and toxicokinetic study in rabbits (23). Additionally, a single-dose (SD) oral vs IV pharmacokinetic study in monkeys was conducted (24). Data on the distribution of EBP-994 are available from a single dose tissue distribution study in pigmented rats (25), a pilot whole body autoradiography (WBA) study in monkeys (26), and in vitro plasma protein binding studies (27, 28). The metabolism of EBP-994 was studied in vitro using liver microsomes, hepatocytes, and recombinant human cytochrome P450 (CYP) isozymes (29, 30, 31, 32). Additional information about the metabolism of EBP-994 was obtained from profiling in rats, monkeys, and humans (33, 34, 35, 36, 37, 38). The routes and extent of excretion of EBP-994 were evaluated in rats, monkeys, and humans (26, 33, 34, 35, 36, 37, 39, 40). The effects of EBP-994 on enzyme induction and enzyme inhibition were studied in vitro (41, 42) and in vivo (19, 21), and the potential for EBP-994 interactions related to transport proteins was also assessed (43, 44, 45).

Pharmacokinetic/toxicokinetic studies in rats, rabbits and monkeys given single and repeated oral doses of EBP-994 suggested slow absorption, with mean  $T_{max}$  = 2-8 hr. The compound had good bioavailability, with a mean absolute oral bioavailability of greater than 65% in rats and monkeys. In both species, increases in plasma AUC with increasing dose were observed but there were also cross-study and cross-species differences in exposure (e.g., sex-dependence) and accumulation patterns.

EBP-994 distributed rapidly into tissues, with liver, adrenal gland, pancreas, bile duct, and kidney reaching maximum concentrations of radioactivity by 4 hr post-dose; the tissue-to-plasma ratios of drug-derived radiocarbon in these tissues at 4 hr ranged from 3.90-14.7. Plasma protein binding to  $^3\text{H}$ -EBP-994 was  $\geq 99\%$  in all species over a 0.5-40.0  $\mu\text{g/mL}$  concentration range and binding to purified serum proteins (HSA, AAG, HSA-AAG) ranged from 94-98%.

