## **6.2 Study Visit 2 (Day 1) - Treatment Period**

This Study Visit marks the beginning of the twenty-four weeks treatment Period in which subjects will receive EBP-994 treatments (EBP-994 alone or in combination with Norvir® and/or Pegasys®). Subjects will be admitted to the unit on the morning of Day 1 in a fasted

state (nothing to eat or drink except water) and will receive a standard breakfast between 45 - 30 minutes prior to scheduled dosing time.

The following evaluations and procedures will be performed at Study Visit 1 (see Appendix A for summary):

1. Brief physical examination pre-dose (performed by a physician, nurse practitioner, physician's assistant or nurse). This includes weight and vital signs as well as HEENT, heart, lungs, abdomen and lower extremity.
2. Vital signs pre-dose and after the post-dose ECG (BP after being seated for 5 minutes, pulse, respiratory rate and temperature)
3. Concomitant medications will be recorded
4. Adverse events will be recorded
5. 12-Lead ECG
6. Randomization

Subjects will be randomized to one of the following groups:

Group 1: EBP-994 (up to 600 mg daily dose) monotherapy  
Group 2: EBP-994 (up to 200 mg daily dose) in combination with Norvir®  
Group 3: EBP-994 (up to 200 mg daily dose) in combination with Pegasys®  
Group 4: EBP-994 (up to 200 mg daily dose) in combination with Norvir® and Pegasys®

7. Laboratory studies (Pre-Dose) (non-fasting):
  - a. Serum chemistry panel, including liver function tests and albumin
  - b. Complete blood count (CBC with differential and platelet count)
  - c. Quantitative PCR for HDV viral load
  - d. Blood samples (plasma and serum) for viral mutation analysis, resistance phenotyping, and analysis of drug mechanism and treatment response. These analyses include molecular and genetic analysis of drug mechanism, viral/host factors influencing treatment response (e.g. genotype and subgenotype analysis, quasispecies analysis, determination of drug and potential metabolite levels in plasma).
  - e. Urinalysis
  - f. Urine pregnancy test (child-bearing females only)

- g. Blood sample for monitoring immunologic changes in peripheral blood mononuclear cells (PBMC).
- 8. Pharmacokinetic blood samples (at the following time points: 0-pre-dose, post dose: 15 min, 30 min, 60 min, 90 min, 2h, 2.5 h, 3 h, 4 h, ,6 h, 8, 10, 12 h) (for those subjects participating in the PK portion of this trial)
- 9. Dosing Instructions:  

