### **8.5.1 PK Linearity and Accumulation Assessment**

The pharmacokinetic parameter  $AUC_{0-t}$  values will be compared against  $AUC_{inf}$  values using an analysis of variance (ANOVA) on the ln-transformed values for EBP-994. The ANOVA model will include Day (Day 1 ( $AUC_{inf}$ ) and Day 28 ( $AUC_{0-t}$ )) as fixed effects. The ANOVA will include calculation of least-squares means (LSM), the difference between day LSM and the standard error associated with this difference. The above statistical analysis will be done using the appropriate SAS® procedure.

*Ratio of LSM will be calculated using the exponentiation of the LSM from the analysis on the ln-transformed response. The ratio will be expressed as a percentage relative to  $AUC_{inf}$  (Day 1).*

Ninety percent confidence interval for the ratio will be derived by exponentiation of the confidence interval obtained for the difference between day LSM resulting from the analysis on the ln-transformed response. The confidence interval will be expressed as a percentage relative to  $AUC_{inf}$  (Day 1).

Accumulation will be evaluated by comparing the plasma exposure of EBP-994 on Day 28 ( $AUC_{0-t}$ ) to the exposure on Day 1 ( $AUC_{0-t}$ ).

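### Subjects with no reportable Day 1 AUCinf still have a Day 28 AUC, and the Day-only linearity ANOVA in Section 8.5.1 is not restricted to subjects with both values

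*Combined protocol and SAP*

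**What the plan says.** **Day 1 (Section 8.5).** No kel, AUCinf or half-life "will be reported for cases that do not exhibit a terminal log-linear phase in the concentration versus time profile". The regression for kel is described by an example, "three or more non-zero plasma concentrations". No goodness-of-fit criterion is given, and the text does not say whether the peak sample may be used.

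**Day 28 (Section 8.5).** The AUC is defined as "The area under the plasma concentration versus time curve over the dosing interval at steady-state, as calculated by the linear trapezoidal method". It does not depend on kel.

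**Comparison (Section 8.5.1).** Day 28 AUC is set against Day 1 AUCinf "using an analysis of variance (ANOVA) on the ln-transformed values for EBP-994". On model terms, the text says "The ANOVA model will include Day" and names no other effect. The result is a ratio of least-squares means: "Ninety percent confidence interval for the ratio will be derived by exponentiation". No acceptance range is given. A separate sentence plans the Day 28 to Day 1 comparison of AUC0-t as the accumulation measure.

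**Sampling (Section 6.2).** Day 1 samples are pre-dose and "post dose: 15 min, 30 min, 60 min, 90 min, 2h, 2.5 h, 3 h, 4 h, ,6 h, 8, 10, 12 h". Footnote 5 of Appendix A lists the same times without the 8 h sample.

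**Absorption (Section 1.2).** The only Tmax in the documents is from animals. Those studies "suggested slow absorption, with mean" Tmax of 2 to 8 h.

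**Missing values (Section 8.9).** Only safety and pharmacodynamic data are covered. PK sampling is optional (Section 3), and the number of PK subjects is not stated.

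**The concern.** A subject whose Day 1 profile shows no terminal phase has no Day 1 value for the linearity comparison. Unless dosed once daily, that subject still has a Day 28 value. (With a 24 h interval, the 12 h sampling does not cover the interval; that is a separate matter.) A Day-only ANOVA fitted to whatever values exist takes the Day 1 mean from one set of subjects and the Day 28 mean from a larger set that contains it.

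This does no harm to the point estimate if loss of AUCinf is unrelated to exposure. There is reason to doubt that. Sampling stops at 12 h, and a slow eliminator declines least by then. Low clearance both hides the terminal phase and raises AUC. A late peak has a similar effect: after a peak at 8 h only the 10 h and 12 h samples remain. On the Appendix A list the same is true after a peak at 6 h.

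PK is among the primary objectives, and this ratio carries the only confidence interval planned in Section 8. A ratio displaced by a change of subjects could be read as a change in clearance over time. Section 1.2 reports in vitro evidence of metabolism-based CYP3A4 inhibition and names CYP3A as the drug's own metabolic route, so such a reading would look credible.

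**Working it through.** The plan gives no expected ratio, variability or sample size, so there is no figure of its own to reproduce.

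**Step 1. Size of the mismatch.** With Day as the only term, the least-squares means are plain means of ln AUC. Let f be the share of PK subjects without AUCinf, and r their geometric mean AUC relative to the rest. Under linear PK, a subject's true Day 28 interval AUC equals the true Day 1 AUCinf. Write m for the mean ln AUC of scored subjects.

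- Day 1 mean = m
- Day 28 mean = (1 − f) × m + f × (m + ln r) = m + f × ln r
- Ratio = 100 × exp(f × ln r)

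At f = 0.30 and r = 1.5: 0.30 × 0.405 = 0.122, and exp(0.122) = 1.129, so 112.9%. Both f and r are assumed.

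| f | r | Ratio when PK is linear |
|---|---|---|
| 10% | 1.5 | 104.1% |
| 20% | 1.5 | 108.4% |
| 30% | 1.25 | 106.9% |
| 30% | 1.5 | 112.9% |
| 30% | 2 | 123.1% |
| 30% | 0.67 | 88.7% |
| any | 1 | 100% |

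**Step 2. Effect on the 90% interval.** Assumed ln-scale SDs are 0.45 between and 0.20 within subjects; 4,000 simulated trials. The Day-only interval wrongly excludes 100% in 11% of trials at n = 20, f = 30%, r = 2; in 38% at n = 40 with the same f and r; and at n = 75 in 24% (f = 30%, r = 1.5) or 81% (f = 30%, r = 2). With f = 0 it almost never does, because ignoring the pairing makes the interval too wide. Analysing only subjects with both values gives 99.6 to 100.3% and excludes 100% in about 10% of trials, the nominal rate. This step contains no error from extrapolating AUCinf.

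**Step 3. Adding extrapolation error.** A linear one-compartment oral model uses the Section 6.2 sample times. Assumed: 12 h dosing interval, 10% assay error, ln-scale SD 0.40 for clearance and 0.50 for absorption rate, and half-life that lengthens as clearance falls. A terminal phase is scored if at least three samples after the peak give a negative slope with adjusted R² of at least 0.8, also assumed.

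| Half-life / absorption half-life | No AUCinf | r | Mismatch alone | Subjects with both values | All available values |
|---|---|---|---|---|---|
| 3 h / 0.7 h | 1.0% | 1.76 | 100.6% | 98.5% | 99.1% |
| 3 h / 2 h | 14.0% | 1.50 | 105.8% | 93.5% | 99.0% |
| 5 h / 0.7 h | 7.1% | 1.69 | 103.8% | 97.8% | 101.5% |
| 5 h / 2 h | 34.6% | 1.41 | 112.6% | 91.5% | 103.0% |
| 8 h / 0.7 h | 22.3% | 1.48 | 109.1% | 97.9% | 106.8% |
| 8 h / 2 h | 57.1% | 1.37 | 119.7% | 90.7% | 108.5% |

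The last column is the product of the two before it, up to rounding: 1.126 × 91.5% = 103.0%. The mismatch pushes up and the extrapolation error pulls down. The net ratio runs from 99.0 to 108.5%.

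**Step 4. Sensitivity to the scoring rule.** Further runs of a linear one-compartment model with 40 PK subjects gave:

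| Setting (assumed) | All available | Both values |
|---|---|---|
| No Norvir effect; post-peak samples and R² ≥ 0.8 required | 101–110% | 91–100% |
| Clearance cut 3- to 5-fold in half the subjects | 109–140% | 92–103% |
| No Norvir effect; no R² rule | 86–99% | 81–99% |

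Without an R² rule, and Section 8.5 has none, the net error is downward. In these runs the Day 28 to Day 1 ratio of AUC over the same observed interval was 125 to 322%, although PK was linear.

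**The case against.** **The text does not say that Day 28-only subjects are kept.** Section 8.5.1 names fixed effects and leaves the SAS procedure open, so a random subject term or complete pairs are not ruled out. This stands. The point therefore concerns an undefined analysis set and what follows if the stated model is run on all available values.

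**The right benchmark is 100%, and the planned analysis may be nearer to it than the paired one.** In runs with 24 or 40 PK subjects, clearance and absorption CV 50%, half-life 4 to 6 h, R² of at least 0.8 and no Norvir effect, the all-available ratio was 101 to 109% and the paired ratio 91 to 97%. The 90% interval wrongly excluded 100% in 0 to 6% of all-available trials but in 18 to 85% of paired trials. This stands as a limit on the fix. It does not justify the present model, whose small net error comes from two unrelated errors cancelling and whose wide interval comes from ignoring the pairing.

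**A reader might infer that the omission pushes the ratio up and produces false non-linearity.** The documents do not support this. The direction of the net error depends on a fit criterion that Section 8.5 does not contain. Its three-point minimum is only an example, and a peak at 8 h leaves three usable samples if the peak itself counts. The 2 to 8 h Tmax is a range of animal means. The largest upward figures need a clearance reduction under Norvir that the documents do not quantify.

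**A reader might also infer that the same-interval AUC ratio should become the main result, since it needs no terminal phase.** Section 8.5.1 already plans it for accumulation. It exceeds 100% under linear PK whenever drug accumulates, so it cannot test linearity.

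**No decision hangs on the ratio.** This is a pilot without power assumptions, and the objectives name the PK profile rather than this contrast. This stands, and limits the harm mainly to a misleading estimate.

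**Conclusion.** The gap is real. Section 8.5 can leave a subject with a Day 28 value and no Day 1 AUCinf, and Section 8.5.1 states neither pairing nor a subject term. If all available values are used, the ratio mixes any true change in exposure with a difference between overlapping subject sets.

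The mismatch component is exp(f × ln r). It is nil if AUCinf is missing independently of exposure, and 113% at the assumed f = 30% and r = 1.5. That missingness relates to exposure is plausible from 12 h sampling and slow absorption in animals, but is not shown for these subjects. The net error cannot be sized or signed from the documents. Without a Norvir effect, the n = 40 simulations gave all-available ratios between 86% and 110%, depending mainly on the assumed scoring rule.

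The supported conclusion is that the linearity ratio has no defined analysis set and should be made within-subject. A claim that the plan will show non-linear PK goes further than the text allows.

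**What to change.** In Section 8.5.1:

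1. Restrict the linearity comparison to subjects with both a Day 1 AUCinf and a Day 28 interval AUC, and add subject to the model.
2. Report by treatment group the number of PK subjects without a Day 1 AUCinf.
3. State that the ratio applies only to subjects with a measurable terminal phase and is still subject to extrapolation error. The ratio of AUC0-t to AUCinf, already planned in Section 8.5, shows how much of each AUCinf is extrapolated and can be presented alongside.
4. Keep the same-interval Day 28 to Day 1 AUC ratio as the accumulation measure for all PK subjects, not as a linearity test.

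The cost is a few sentences and one extra line per PK table, with no new samples or visits. Fewer Day 28 values enter the linearity ratio. The paired interval will also be narrower, so extrapolation error alone may make it exclude 100%; item 3 is needed for that reason.

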### **8.5.1 PK Linearity and Accumulation Assessment**

The pharmacokinetic parameter  $AUC_{0-t}$  values will be compared against  $AUC_{inf}$  values using an analysis of variance (ANOVA) on the ln-transformed values for EBP-994. The ANOVA model will include Day (Day 1 ( $AUC_{inf}$ ) and Day 28 ( $AUC_{0-t}$ )) as fixed effects. The ANOVA will include calculation of least-squares means (LSM), the difference between day LSM and the standard error associated with this difference. The above statistical analysis will be done using the appropriate SAS® procedure.

*Ratio of LSM will be calculated using the exponentiation of the LSM from the analysis on the ln-transformed response. The ratio will be expressed as a percentage relative to  $AUC_{inf}$  (Day 1).*

Ninety percent confidence interval for the ratio will be derived by exponentiation of the confidence interval obtained for the difference between day LSM resulting from the analysis on the ln-transformed response. The confidence interval will be expressed as a percentage relative to  $AUC_{inf}$  (Day 1).

Accumulation will be evaluated by comparing the plasma exposure of EBP-994 on Day 28 ( $AUC_{0-t}$ ) to the exposure on Day 1 ( $AUC_{0-t}$ ).

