CYP 3A (3A4 and 3A5) is responsible for the oxidative metabolism of EBP-994 (29, 31). Studies of CYP inhibition indicate that the CYP3A4 IC50 = 10.2  $\mu\text{g/mL}$  and CYP2C9 IC50 = 16  $\mu\text{g/mL}$  (24), showing that the one-half maximal inhibition is achieved at three to five times the mean human plasma Cmax (2.8  $\mu\text{g/mL}$ ) at 200 mg BID (46, 47, 48). Preincubation of human liver microsomes for 15 min with EBP-994 decreased the IC50 for inhibition of CYP3A4, suggesting a metabolism-based inhibition. In vitro inhibition of activity of other CYP enzymes (1A2, 2C19, 2D6) by EBP-994, however, does not appear to occur to an extent likely to suggest a risk of adverse events in humans.

In ancillary pharmacology studies in rats, EBP-994 was well tolerated over the oral dose range of 30 to 300 mg/kg. It was devoid of gastric ulcerogenicity and adverse effects on CNS function, but exhibited moderate inhibition of GI motility at high doses ( $\geq 100$  mg/kg). Clinical findings consistent with a decrease in GI motility have not been observed with EBP-994. Urine chemistry parameters showed a decrease in sodium and potassium excretion at 300 and 500 mg/kg and a reduction in creatinine clearance at 500 mg/kg. At doses of 500 mg/kg orally, rats were moribund and displayed a variety of adverse effects. Repeated oral

dosing of EBP-994 to monkeys at 60 mg/kg for 7 days caused diarrhea, emesis, weight loss, thrombocytopenia and an elevation of AST.

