## 2 STUDY OBJECTIVES

The primary objectives of the study are to:

- Evaluate the safety and tolerability of 12 weeks of treatment with either a 200 mg po BID dose of EBP-994, or a 300 mg po BID dose of EBP-994, in subjects chronically infected with HDV genotype 1
- Evaluate the pharmacodynamic (PD) activity of a 200 mg po BID dose of EBP-994, vs. a 300 mg po BID dose of EBP-994 on HDV viral load
- Evaluate the pharmacokinetic (PK) profile of a 200 mg po BID dose of EBP-994 vs. a 300 mg po BID dose of EBP-994 in subjects chronically infected with HDV genotype 1
- Evaluate the safety, tolerability, PK, and HDV viral load of a treatment up to 48 weeks with EBP-994 alone, or in combination with Norvir® and/or Pegasys® in subjects chronically infected with HDV

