## 3 STUDY DESIGN

This study is a phase II, randomized, open label study of up to 48 weeks of treatment with EBP-994 alone, or in combination with Norvir® and/or Pegasys® in subjects chronically infected with HDV genotype 1. The investigator is free to initiate licensed medications at any time point and decrease the dose of EBP-994 if deemed warranted for GI side effects. The duration of the study for each subject will be approximately 11-55 weeks (up to three week screening period, up to 48 week treatment period and four week safety follow-up period).

The duration of the entire study is anticipated to be approximately 36 months (first subject in to last subject out). Pharmacokinetic sampling will be done at Day 1 and Day 28 of dosing. PK sampling will be conducted only on subjects who have consented to participate in the PK portion of this study. Participation in PK sampling is optional for each subject.

At the Screening Visit, subjects giving written informed consent will have all required evaluations to determine their eligibility to participate in the study. The outpatient screening visit must occur within 21 days of Study Visit 1.

Each eligible subject will undergo 8-16 Study Visits; Screening, Day 1, Day 2, Day 3, Day 7, Day 14, Day 28, then every 4 weeks (total duration depends on assigned treatment group), followed by a Safety Follow-Up Visit, 4 weeks post-treatment. Study drug will consist of EBP-994 alone or in combination with either Norvir® and/or Pegasys®, depending on which group the subject has been randomized to on the Day 1 visit. Moreover, the investigator is free to initiate licensed medications at any time point and decrease the dose of EBP-994 if deemed warranted for GI side effects.

During the intervals between Study Visits, subjects will be free to carry on their usual activities of daily living. Subjects will be instructed to take their study medication at appropriate dosing intervals. Efforts should be made to schedule Study Visits according to the study protocol; however the window for consecutive Study Visits will be  $\pm 2$  days with the exception of Day 2 and Day 3 for which a visit window is not allowed.

Safety will be monitored by assessing vital signs, adverse events, concomitant medications, laboratory and ECG results. ECGs will be conducted and vital signs assessed at each Study Visit.

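### The Section 8.5.1 ANOVA names no subject term for paired AUCs, so its 90% CI over-covers at any positive within-subject correlation; separately, AUC is not dose-normalised although doses may fall between the two days

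*Combined protocol and SAP*

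**What the plan says.** Section 8.5.1 sets Day 28 AUC over the dosing interval against Day 1 AUCinf in an ANOVA of ln-transformed values. The model is given in one sentence: "The ANOVA model will include Day (Day 1 ( $AUC_{inf}$ ) and Day 28 ( $AUC_{0-t}$ )) as fixed effects". The ratio of least-squares means and its 90% confidence interval come from the Day difference, using whatever SAS procedure is appropriate. No subject effect, repeated-measures structure, dose term or group term is named, and AUC is not divided by dose. Accumulation is a separate comparison, with no interval planned: "Accumulation will be evaluated by comparing the plasma exposure of EBP-994 on Day 28", against Day 1 AUC0-t.

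Section 3 sets the sampling: "Pharmacokinetic sampling will be done at Day 1 and Day 28 of dosing", in subjects who consent to the optional PK part. So each PK subject contributes both values by design. The same section leaves the investigator "free to initiate licensed medications at any time point and decrease the dose of EBP-994" for GI side effects.

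Section 8.5 withholds kel, AUCinf and half-life when a profile shows no terminal log-linear phase, and lists the ratio of AUC0-t to AUCinf as a Day 1 parameter. Section 5.2 allows 8, 12 or 24 h dosing. Sections 6.2 and 6.7 end the PK profile at 12 h. Section 8.7 makes no assumption about variability.

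**The concern.** The Day 28 to Day 1 contrast lies within subjects. A model with Day alone treats the two sets of AUCs as independent samples and charges the contrast with differences between subjects that cancel within each pair. Those differences are likely to matter, because subjects on different doses are pooled with no dose or group term.

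This is the only confidence interval planned in Section 8, and the only planned inferential look at whether clearance changes over 28 days. PK is among the primary objectives ("Evaluate the pharmacokinetic (PK) profile of a 200 mg po BID dose of EBP-994 vs. a 300 mg po BID dose"), and Section 1.2 gives a reason to ask. CYP3A "is responsible for the oxidative metabolism of EBP-994", and preincubation with EBP-994 lowered the IC50 "for inhibition of CYP3A4, suggesting a metabolism-based inhibition". An interval that is too wide makes a real change in clearance harder to see.

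The second matter is separate. If the dose falls before Day 28, the unnormalised ratio mixes the dose change with any change in clearance.

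**Working it through.** The plan states no figure to reproduce; Section 8.5.1 fixes only the 90% level. All inputs below other than that level and the 200 and 300 mg doses are assumptions: n = 15 PK subjects, total CV 50%, and within-subject correlation ρ from 0 to 0.7. On the log scale, σ = √ln(1 + 0.5²) = 0.472.

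**1. Width, complete pairs**
- Day-only half-width: t(0.95, 2n−2) · σ · √(2/n).
- Paired half-width: t(0.95, n−1) · σ · √(2(1−ρ)/n).
- Their ratio: [t(0.95, 28) / t(0.95, 14)] / √(1−ρ) = (1.701 / 1.761) / √(1−ρ) = 0.966 / √(1−ρ).
- Results: 0.97 at ρ = 0, 1.37 at ρ = 0.5, 1.76 at ρ = 0.7.
- At a true ratio of 100%, a typical Day-only interval is exp(±1.701 × 0.472 × √(2/15)), or 75% to 134%. The paired interval is 81% to 124% at ρ = 0.5 and 85% to 118% at ρ = 0.7.

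**2. Break-even**
- Setting the width ratio to 1 gives ρ = 1 − [t(0.95, 2n−2) / t(0.95, n−1)]².
- n = 4: 1 − (1.943/2.353)² = 0.32.
- n = 6: 1 − (1.812/2.015)² = 0.19.
- n = 15: 1 − (1.701/1.761)² = 0.07.
- Below these correlations the paired interval is slightly the wider, because it has fewer degrees of freedom.

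**3. Coverage and power (simulation, bivariate normal, n = 15)**

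| ρ | Day-only coverage | Paired coverage | Lower limit above 100% when true ratio is 125%: Day-only / paired |
|---|---|---|---|
| 0 | 90% | 90% | 35% / 34% |
| 0.5 | about 97.5% | 90% | 30% / 54% |
| 0.7 | 99.4% | 90% | 26% / 73% |

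**4. Point estimate**
- With complete pairs, the difference of the two Day means equals the mean of the within-subject differences. Adding subject leaves the ratio unchanged.

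**5. Dose change**
- If a share f of subjects goes from 300 to 200 mg and clearance is constant, the unnormalised ratio reads (2/3)^f.
- f = 0.25: 90%. f = 0.40: 85%.
- With 6 of 15 subjects reduced and ρ = 0.7, coverage of the true 100% is 91% Day-only and 60% paired without normalisation. Pairing alone therefore tightens the interval around a biased ratio.

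**6. Limit of dose normalisation**
- It assumes AUC proportional to dose. If AUC instead rose as dose^1.5 (assumed), the normalised ratio would read (2/3)^(0.5f): 95% at f = 0.25 and 92% at f = 0.40.

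**The case against.** The strongest reply is that the sentence lists fixed effects only, so a random or repeated subject term need not appear there, and the SAS procedure is left open. That is fair as far as it goes: the text does not forbid a subject term. But nothing names one, and a choice of software does not specify an error structure. Followed as written, the model has Day alone.

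The error is also conservative for random variation, the study is a pilot, and no acceptance limits are set. These points lower the consequence but do not make the interval a 90% interval.

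A reader might infer more than the documents support:
- **That the interval is wider than the paired one at every positive correlation.** It over-covers at every positive correlation. It is wider than the paired interval only above the break-even in step 2.
- **That AUCinf from a 12 h profile badly distorts the ratio.** Section 1.2 reports that animals "given single and repeated oral doses of EBP-994 suggested slow absorption", with mean Tmax of 2 to 8 h. A one-compartment calculation can bring the ratio down to 78% to 80% at a 6 h peak, but only by forcing kel through the last three samples. Section 8.5 restricts the fit to the terminal log-linear phase and withholds AUCinf without one. At peaks of 2 to 3 h the same calculation is off by at most 1%.
- **That 8 h dosing feeds invalid AUCinf values into the ANOVA.** In that calculation the 8 to 12 h slope rises after the second dose, so Section 8.5 would already withhold AUCinf. What remains is the Day 1 AUC0-t used for accumulation.
- **That missing AUCinf biases the ratio.** This needs the loss to be related to exposure. Section 8.5 ties it to profile shape, and the documents give no link to exposure.

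**Conclusion.** The concern holds in two parts. First, the model as written omits subject for paired data, so its nominal 90% interval over-covers at any positive correlation: about 97.5% at 0.5 and 99.4% at 0.7 for 15 subjects, with widths 1.37 and 1.76 times the paired ones. The loss is in precision; with complete pairs the estimate does not move. Second, AUC is not dose-normalised although the protocol permits dose reduction between the days, which would make linear PK read 90% to 85% if 25% to 40% of subjects went from 300 to 200 mg.

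The number of PK subjects, variability, correlation and share of dose reductions are all assumed, so the sizes are illustrative. The directions of both effects do not depend on them, given a positive correlation. A reader might infer that the study's conclusions are at risk. The documents do not support that: no decision is tied to this interval, accumulation is not read from it, and the descriptive PK tables do not use it. The change should still be made, because it costs little and this is the plan's only interval.

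**What to change.** In Section 8.5.1:
- Add subject to the model, either as a paired analysis of subjects with both values or as a mixed model with random subject.
- In the same change, analyse ln of dose-normalised AUC. Neither change should be made alone.
- Report alongside it the same paired analysis restricted to subjects whose EBP-994 dose and co-medication did not change, because normalisation assumes exposure proportional to dose.
- Prestate a limit on the extrapolated share of AUCinf, which is one minus the AUC0-t/AUCinf ratio already planned, and repeat the analysis without subjects above it.
- Compute the accumulation ratio over the same dosing interval on both days. Under 8 h dosing, leave out Day 1 samples taken after the second dose. Under 24 h dosing, do not report a full-interval AUC from a 12 h profile.

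The cost is wording; no new samples are needed. Subjects without both values leave the paired analysis, and some degrees of freedom are lost (14 instead of 28 at n = 15), which matters only at very small n with weak correlation. The restricted analysis will be smaller still.
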